6.1 Screening Procedure and Study Visits

The Time of Events Schedule (for Groups 1, 2, and 3) summarizes the frequency and timing of various study assessments. See **Appendix A**.

6.1.1 Pre-Screening Questionnaire

Potential participants will first undergo pre-screening by telephone to assess medical history, preliminary HIV risk assessment, and qualification for the study. Potential participants will have the opportunity to discuss the study and ask questions of the study recruiter at this time. Those who are eligible and interested in participation will attend a screening visit at the Rockefeller University Hospital (RUH) Outpatient Clinic.

6.1.2 Screening Visit

Initial Screening Visit:

Study personnel will answer any questions about the study. Written informed consent will be obtained prior to conducting any study procedures. To insure informed consent, the principal investigator or designee will discuss the following processes individually with each potential participant:

- 1. HIV-test counseling;
- 2. Risk-reduction counseling including safe-sex and pregnancy avoidance counseling;
- 3. That sexually active males and females, participating in sexual activity that could lead to pregnancy, should use two reliable forms of contraception for the duration of the trial.

If the potential participant consents to participate, site personnel will:

- Perform detailed HIV risk assessment;
- Perform complete medical history (including review of concomitant medication);
- Perform a general physical examination including height, weight, vital signs (pulse, respiratory rate, blood pressure and temperature), examination of skin, respiratory, cardiovascular and abdominal systems;
- A point of care hemoglobin test may be performed to expedite screening;
- Collect blood and urine specimens for all tests as indicated in the Time of Events Schedule (Appendix A);
- Perform a pregnancy test for all female participants.
- Participants that meet eligibility criteria will have an ophthalmologic assessment (including slit lamp examination) at no cost to the participant

If the initial screening visit occurs more than 49 days prior to date of the first mAb infusion, then laboratory tests (blood and urine specimens) for the screening visit must be repeated. The most recent set of results will be used.

6.1.3 **3BNC117/10-1074** Infusion Visit

Prior to 3BNC117/10-1074 infusions, site personnel will:

- Review the informed consent form administered at screening visit with the participant;
- Answer any questions about the study;
- Review interim medical history (including concomitant medications);
- Review safety laboratory data;
- Perform a physical examination including weight, vital signs (pulse, respiratory rate, blood pressure and temperature) and any further examination indicated by history or observation;
- Collect blood and urine specimens for all tests as indicated in the Time of Events Schedule (Appendix A);
- Perform pregnancy counseling;
- Perform a pregnancy test for all female participants and obtain results prior to drug infusion;
- Perform baseline assessment and record any systemic symptoms;
- 3BNC117 and 10-1074 will be prepared for administration according to the RUH Pharmacy Standard Operating Procedures;
- 3BNC117 will be administered via a peripheral vein over 60 minutes. The IV line will be flushed with normal saline after infusion is completed;
- 10-1074 mAb will be administered after 3BNC117 infusion is completed and the line is flushed with normal saline. It will be infused via a peripheral vein over 60 minutes. The IV line will be flushed with normal saline after infusion is completed;
- Study participants in Group 1 will be observed for 4 hours after the 10-1074 infusion is completed. Presence or absence of adverse events will be recorded at 1 and 4 hours post infusion; study participants in Groups 2 and 3 will be observed for

1 hour. Presence or absence of adverse events will be recorded at 1 hour post infusion.

- Vital signs (pulse, respiratory rate, blood pressure and temperature) will be monitored at end of 3BNC117 infusion, at the end of 10-1074 infusion, 1hr (+/- 5 minutes) and 4 hrs (+/-10 min; group 1 only) post 10-1074 infusion.
- If participants develop acute infusion reaction during 3BNC117 or 10-1074 administration, the infusion will be discontinued and will not be reinitiated. If the acute infusion reaction occurs during 3BNC117 infusion, 10-1074 will not be infused. Rescue medications, including acetaminophen, diphenhydramine and glucocorticoids will be available in the RUH inpatient unit for use if clinically indicated.

6.1.4 Post-3BNC117/10-1074 Administration Visits

Participants will be followed for 24 weeks after the last 3BNC117 and 10-1074 infusions.

At these follow up visits the following will be conducted:

- Review of interim medical history and use of concomitant medications;
- If symptoms are present, perform a symptom-directed physical examination;
- Local and systemic reactogenicity adverse events, as well as other adverse events, will be assessed;
- Pregnancy and safe sex counseling;
- Vital Signs;
- Collect blood and urine specimens for all tests as indicated in the Time of Events Schedule (Appendix A);
- In case of adverse event(s), the participant will be assessed and followed up by the clinical team. Supplemental visit(s) for further investigation can be planned at the discretion of the principal investigator or designee. Supplemental visit(s) may be recommended if clinically indicated or to clarify observations.
- Any participant that develops signs or symptoms of ocular disease will be promptly referred to an ophthalmologist for diagnosis and management
- Participants in Group 1 will have scheduled ophthalmologic exams at Day 28; participants in Groups 2 and 3 will have a scheduled ophthalmologic exam at Week 20 (28 days following the third dose).

Specific procedures to be performed at each follow up visit for Groups 1, 2, and 3 are illustrated in the Time of Events Schedules (**Appendix A**).

Any abnormalities (adverse events) attributed to study drug, including laboratory abnormalities, should be subsequently followed until the event or its sequelae resolve or stabilize.

6.1.5 Final Visit/Early termination Visit

Assessments will be undertaken according to the Time of Events Schedule (Appendix A).

6.1.6 Unblinding

After all participants have completed the final study visit, participants will be informed as to whether they received the study product or placebo. This will be performed by phone.

6.1.7 Discontinuation of 3BNC117/10-1074 infusion and/or participant withdrawal from study

6.1.7.1 Discontinuation of 3BNC117/10-1074 infusions

Antibody infusion will be discontinued for any of the following reasons:

- 1. Any immediate hypersensitivity reaction (such as urticarial rash; bronchospasm; laryngeal edema; anaphylaxis; syncope).
- 2. Life threatening medical event during 3BNC117 or 10-1074 infusion.

6.1.7.2 Discontinuation from subsequent 3BNC117/10-1074 infusions

Participants will be discontinued from second or third 3BNC117/10-1074 infusions for any of the following reasons:

- 1. A disease or condition or an adverse event that may develop, regardless of relationship to 3BNC117 or 10-1074, if the principal investigator or designee is of the opinion that other 3BNC117 or 10-1074 infusions will jeopardize the safety of the participant.
- 2. Any immediate hypersensitivity reaction (such as urticarial rash; bronchospasm; laryngeal edema; anaphylaxis; syncope).
- 3. Any grade 2 ophthalmologic adverse event deemed related to the study products, or any grade 3 or 4 ophthalmologic adverse event regardless of causality assessment.
- 4. Any ALT or AST increase equal to or greater than 3x the upper limit of normal with concurrent increase in total bilirubin equal to or greater than 2x the upper limit of normal. Additionally, such an occurrence will also result in a consultation with a hepatologist to assess for other evidence of drug toxicity.
- 5. Any participant with a graded elevation in total bilirubin will undergo a diagnostic workup at no cost to the participant that includes right upper quadrant ultrasound, testing for gamma glutamyl transferase (GGT), HAV, HBV, HCV, EBV serologies, CMV serologies, VZV serologies, HSV serologies, and any other relevant laboratory tests as determined by the investigators. Further administration of the investigational products will be discontinued for any participant with a grade 3 or above elevation in total bilirubin for whom this evaluation fails to determine the etiology.
- 6. Life threatening medical event following 3BNC117 and/or 10-1074 unless not related to the investigational product.
- 7. Intercurrent use of immunosuppressive medication considered significant by the trial physician (e.g., systemic corticosteroids).
- 8. Pregnancy.
- 9. Participant's request to discontinue further 3BNC117 or 10-1074 infusions.

- 10. A participant in Groups 2 or 3 who misses the second dose of mAbs or placebo will not receive the third dose.
- 11. Any participant who misses an infusion will not attend the Day +2 visit following the missed dose.

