6.1.7.3 Withdrawal from the study (Early Termination)

Participants may be withdrawn from the study permanently for the following reasons:

- 1. Participants may withdraw from the study at any time if they wish to do so, for any reason.
- 2. Following an adverse event at the discretion of the investigator (or designee).
- 3. Intercurrent HIV infection.
- 4. Participant judged by the investigator to be at significant risk of failing to comply with the protocol in a manner that might lead to harm to self or seriously interfere with the validity of the study results.
- 5. At the discretion of the FDA or investigator.

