1. If > 1 grade 3 or higher adverse events deemed probably or definitely related to the study drugs occur in a single group, no additional administration of the investigational product will take place pending a Safety Monitoring Committee (SMC) review. The SMC will provide a recommendation regarding subsequent enrollment in the study.

2. If there is one SAE judged as possibly, probably or definitely related to the administration of 3BNC117 and/or 10-1074 by the principal investigator or designee, no additional administration of the investigational product will take place pending a review by at least two members of the SMC. Following this review, the SMC will make a recommendation to the principal investigator regarding the continuation of investigational product administration.

SAEs, which are deemed possibly, probably or definitely related to 3BNC117 and/or 10-1074 by the principal investigator or designee, and unanticipated adverse events will be reported to the SMC within 2 working days of the site becoming aware of the event.

3. If, at any time, a fatal, life-threatening or permanently disabling SAE with a suspected causal relationship to 3BNC117 and/or 10-1074 occurs, no further administration of the

investigational products will occur until a consensus plan forward has been approved by investigators, SMC, the IRB, and the FDA.

4. The SMC will be informed within 2 working days of any participant who discontinues study treatments as a result of a grade 2 ophthalmologic adverse event deemed related to the study products or a grade 3 or 4 ophthalmologic adverse event deemed unrelated to the study drugs.

5. The SMC will be informed within 2 working days of any participant who discontinues receipt of the study products as a result of liver test abnormalities as described in Section 6.1.7.2.

6. In addition, the SMC will be asked to review on an interim basis:

- Severe solicited and unsolicited adverse events judged by the principal investigator or designee to be possibly, probably or definitely related to 3BNC117 and/or 10-1074.

- Severe laboratory adverse events confirmed on retest and judged by the principal investigator or designee to be possibly, probably or definitely related to 3BNC117 and/or 10-1074.

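### The bilirubin stop in 6.1.7.2 item 5 asks whether the workup found a cause, not whether that cause is unrelated to the study products

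*Protocol*

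**What the plan says.** Protocol section 6.1.7.2 lists the reasons for which a participant will not receive a second or third infusion. Item 5 requires a diagnostic workup for any graded rise in total bilirubin: an ultrasound, GGT, a set of viral serologies, and whatever other laboratory tests the investigators consider relevant. It then mandates a stop for a participant with a "grade 3 or above elevation in total bilirubin for whom this evaluation fails to determine the etiology".

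The neighbouring items treat causality differently:

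- Item 1 applies whatever the relationship to the product, but only "if the principal investigator or designee is of the opinion that other 3BNC117 or 10-1074 infusions will jeopardize the safety of the participant".
- Item 3 stops for "any grade 3 or 4 ophthalmologic adverse event regardless of causality assessment".
- Item 4 stops for "Any ALT or AST increase equal to or greater than 3x the upper limit of normal with concurrent increase in total bilirubin" to at least twice the upper limit.
- Item 6 stops for a "Life threatening medical event following 3BNC117 and/or 10-1074 unless not related to the investigational product".
- Item 10 adds that a participant in Group 2 or 3 "who misses the second dose of mAbs or placebo will not receive the third dose".

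Section 6.1.7.3, item 2, also allows withdrawal from the study: "Following an adverse event at the discretion of the investigator (or designee").

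At study level, section 13.1 halts dosing pending committee review "If > 1 grade 3 or higher adverse events deemed probably or definitely related to the study drugs occur in a single group" (item 1), or after one related serious adverse event (item 2). Item 5 of 13.1 gives the Safety Monitoring Committee (SMC) two working days' notice of a discontinuation for liver tests. Item 6 gives it interim review of severe related laboratory events, with no automatic pause.

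**The concern.** Item 5 sets two conditions for the stop: the elevation is grade 3 or above, and the workup has not found its cause. Finding a cause lifts the mandatory stop, whatever the cause is. A cause that lies with the study products, or may do so, is the one that should count most against re-dosing, yet read literally it removes the obligation to stop. Item 6 of the same list avoids this by making an exception only for events that are not related.

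What is at stake is the safety of individual participants in the repeat-dose groups. Section 12 says that the two antibodies have not been given together before and that three doses of 10-1074 have not been given before. A hard stop exists so that the outcome does not depend on one person's judgement, and here it omits a case that it was probably meant to include.

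**Working it through.** No figure in the protocol bears on this rule. The check is one of logic, followed by a count of exposure.

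**Step 1. Item 5 taken case by case, for a grade 3 or above elevation.**

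| Workup result | Investigator's relatedness judgement | Mandatory stop under item 5 as written | With the proposed clause |
|---|---|---|---|
| No cause found | Unrelated | Yes | Yes |
| No cause found | Related | Yes | Yes |
| Cause found, unrelated to the products | Unrelated | No | No |
| Cause found, product-related or possibly so | Related or uncertain | **No** | **Yes** |

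Only the last row changes. The second row matters: a relatedness judgement is a separate step from the workup, so a negative workup leads to a stop even when the investigator blames the antibodies.

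**Step 2. Can the last row occur?** The named tests look for non-drug causes, so they are unlikely to point to an antibody. The list is open-ended, however. As an illustration of mine, not taken from the protocol, an added test might show haemolysis. That would explain the rise without settling whether the antibodies provoked it.

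**Step 3. Does another mandatory rule cover one isolated, non-serious case of this kind?**

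- 6.1.7.2 item 4: no, it needs ALT or AST at 3 times the upper limit or more.
- 6.1.7.2 item 6 and 13.1 item 3: no, they need a life-threatening event or, for 13.1 item 3, also a fatal or permanently disabling one.
- 13.1 item 1: no, it needs more than one probably or definitely related grade 3 or higher event in a group.
- 13.1 item 2: no, its halt needs a serious adverse event.
- 13.1 item 6: review only, with a pause if the investigator judges that risk has increased or if the IRB, SMC or FDA recommends it.
- 6.1.7.2 item 1 and 6.1.7.3 item 2: both rest on investigator judgement.

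**Step 4. Notice to the SMC.** The notice in 13.1 item 5 follows a discontinuation, so it is not triggered while dosing continues. If the event is unanticipated, 13.1 item 2 and 13.5 still bring it to the SMC within two working days.

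**Step 5. Exposure.** Group 1 has a single infusion, so only Groups 2 and 3 matter (sections 6.2.2 and 7.1: 6 active and 2 placebo participants per group, three infusions each).

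- Further visits for one affected participant: 3 − 1 = 2 if the event follows infusion 1, and 3 − 2 = 1 if it follows infusion 2.
- All re-dosing visits: active 2 × 6 × 2 = 24, placebo 2 × 2 × 2 = 8, total 32. This is total exposure, not an estimate of affected visits.
- The protocol gives no rate of grade 3 or above bilirubin. Assuming a rate p per participant, the chance of at least one such elevation among 12 active participants is 1 − (1 − p)^12. That is 1.2% at p = 0.1% and 11.4% at p = 1%. The cases in the last row of the table are a subset, so their chance is smaller, by an amount that the protocol does not allow one to state.

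**The case against.** The strongest reply is that the case hardly arises and would be handled if it did.

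Item 5 refers to what the evaluation determines, and an investigator's attribution is not that evaluation. Section 6.2.2 keeps investigators blinded, with 2 of 8 participants per group on placebo and unblinding only in a medical emergency, so they can suspect the product but can seldom establish it as the cause. An investigator who had established it would very likely stop under item 1. Reporting does not depend on 13.1 item 5 alone either.

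Most of this stands, and it rules out three stronger readings that a reader might infer:

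- *That any grade 3 bilirubin rise attributed to the antibodies is left to judgement.* It is not: attribution after a negative workup still leads to a mandatory stop.
- *That the protocol calls for re-dosing or has no safeguard.* It does neither: item 1, SMC review and the study-level rules remain.
- *That the SMC would not hear of such a case.* It would within two working days if the event is unanticipated, and through interim review if it is severe, related and confirmed on retest.

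What does not stand is the conclusion that nothing needs correcting. Blinding makes it hard to prove that an antibody was the cause, but it does not prevent a workup from finding a mechanism that may be product-related. Such a finding is enough to take the case out of item 5. Reliance on item 1 then replaces a fixed rule with opinion in the case where the fixed rule has most reason to apply.

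**Conclusion.** The point holds in a narrow form. Item 5 tests whether a cause was found, when it should test whether the cause is unrelated. The intent was probably to stop unless another explanation emerged, and in most product-caused cases the present wording would have that effect. The gap is confined to an isolated, non-serious elevation of grade 3 or above in Group 2 or 3 for which the workup establishes a cause that is, or may be, product-related.

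The consequence is at most two further infusion visits for such a participant, decided on opinion. No endpoint, sample size or analysis is affected, and the correction is desirable rather than essential.

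The conclusion rests on a literal reading of item 5. The event rates above are assumptions and do not measure the gap itself. The grading scale in Appendix B is not in the text available, so it cannot be checked whether a grade 4 value would count as life-threatening under item 6, which would narrow the gap further.

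**What to change.** In the last sentence of 6.1.7.2 item 5, keep the threshold of grade 3 or above and replace the qualifier about an undetermined etiology with: *unless this evaluation establishes a cause unrelated to the investigational products*. This borrows the causal test that item 6 already uses. Section 13.1 needs no change, because its item 5 then covers these discontinuations.

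The cost is one clause and no new procedures. The downside is an occasional extra discontinuation; if it follows the first infusion, the participant loses the second dose and, with item 10, the third.

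A hold on infusions while the workup is pending is a separate, optional addition. If adopted, it should be limited to grade 3 or above, because item 5 requires a workup for any graded rise and a wider hold could cost doses needlessly. Such holds should seldom delay dosing. Section 4 schedules safety bloods at weeks 1, 2 and 4 after each infusion, which leaves 8 − 1 = 7, 8 − 2 = 6 or 8 − 4 = 4 weeks before the next one. A rise found later would leave less time.

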6.1.7.3 Withdrawal from the study (Early Termination)

Participants may be withdrawn from the study permanently for the following reasons:

- 1. Participants may withdraw from the study at any time if they wish to do so, for any reason.
- 2. Following an adverse event at the discretion of the investigator (or designee).
- 3. Intercurrent HIV infection.
- 4. Participant judged by the investigator to be at significant risk of failing to comply with the protocol in a manner that might lead to harm to self or seriously interfere with the validity of the study results.
- 5. At the discretion of the FDA or investigator.

6.1.7.4 Follow up after withdrawal from study (Early Termination)

Any adverse event resulting in withdrawal of a participant will be followed up until resolution or until the adverse event is judged by the principal investigator or designee to have stabilized where possible.

At the time of withdrawal, provided the participant is willing, all the requested termination visit procedures will be performed according to the Time of Events Schedule (**Appendix A**).

The date and reason for withdrawal from the study (early termination) should be collected and reported to the SMC, the Clinical Research Support Office (CRSO) at the Rockefeller University Hospital and the RUH-IRB. Participants who are withdrawn from the study (early termination) will not be replaced, but, wherever possible, will be followed until the time of their final planned visit.

A pregnant participant will not receive 3BNC117 or 10-1074 infusion. If pregnancy occurs after 3BNC117 or 10-1074 infusion, no further infusions will be administered, and the participant will continue to be followed until the end of the study and until delivery, if delivery occurs after the study has ended. Approximately 2-4 weeks after delivery, a pediatrician of the participant's choosing will assess the infant's health status. Rockefeller University will subsidize the cost of this visit. The health status of the infant will be reported to the RUH-IRB, CRSO and the SMC.

6.2 Study Procedures

6.2.1 Consent Procedure

Prior to the initiation of any study related procedures, the potential participants will be given a copy of the most recent IRB stamped and approved informed consent to read. Additionally, the PI or study staff member who has been designated to consent will discuss the specifics of the study including but not limited to the purpose of the research, procedures, time commitment, required tasks, test article, alternative treatments, benefits, risks, confidentiality etc. in a comprehensible (non-scientific) manner, using language readily understandable by the participant. Participants will be told that participation is voluntary and that, if they do not consent, they will not be penalized. The person consenting will assure the voluntariness of the participant.

A private, confidential setting will be provided for the potential participant to read and discuss the informed consent free from coercion, undue influence or constraints of time. All participants will be given a chance to ask questions and express concerns. They will be given the option to take the consent home and discuss it with family, friends, and /or health care providers. After a participant and the person conducting the consenting process sign and date the consent, the participant will be given a copy of the signed informed consent form.

An enrollment note will be written in the source document as to who obtained consent, how, when, were questions asked and answered, and that a copy of the informed consent was given to the participant.

The "Teach Back" method will be used in the clinical research setting to ask research participants to repeat or "teach back" the information, concepts and directions that the staff member has attempted to convey to the participant. This method is used to assess comprehension and retention of protocol requirements, adverse event information, risks and benefits, and the participant's rights described in the Informed Consent process.

